One of the main features of this novel, cross-disciplinary concentrated intervention (lasting less than a week) is a shift in focus from targeting symptoms to targeting and monitoring everyday micro-choices that facilitate increased levels of functioning. The intention of these micro-choices is to break inflexible patterns of symptom regulation by “doing something different” whenever tempted to be guided by the symptoms. This approach enables the patient to systematically increase flexibility and their level of functioning when the symptoms and health challenges are present. In addition, a focus on deliberate behavior instead of symptoms, implies that change is within reach and possible to control.

In order to ensure a safe setting in which participants may challenge their current coping strategies, they will work together with an interdisciplinary team and each patient will design individually tailored plans for the most relevant micro-choices. To ensure that the patients are prepared to initiate change, they are thoroughly introduced to the program prior to treatment, and if reluctant, they are encouraged to postpone participation until ready. After the concentrated intervention, the patients will be prepared to integrate the changes as part of their everyday living.

The aim of this pilot study is to explore the acceptability of the concentrated interdisciplinary group rehabilitation for patients with chronic low back pain, post-COVID-19 symptoms, anxiety and depression, and diabetes type 2, and describe basic changes in functional status. Based on our experiences with other concentrated treatment formats, we expect the intervention to be highly acceptable and to have significant effects on functional impairment [15–19].

Main hypotheses

- The treatment will be acceptable for the patients, regardless of illness, and they will complete the treatment
- Patients will be satisfied with the treatment

- There will be a significant reduction in how much the illness affects the patients' life
- The patients' level of functioning will be improved at follow-up.

Methods

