videos describing the program, to ensure that all participants receive the same information (at the homepage www.helseihardanger.no) [22]. For low-back pain and diabetes type 2 the informed consent will be signed online, while patients with post-COVID-19 symptoms or anxiety/depression will sign at baseline testing, when the first face-to-face meeting takes place. For low-back pain and diabetes type 2, participants will be invited in groups to an approximately two-hour meeting 1-3 weeks before the treatment to make sure that they are prepared for the intervention. For patients suffering from anxiety and depression, or post-COVID-19 symptoms, the same information will be provided individually during the screening. All patients will be contacted by a therapist during the week prior to the treatment to confirm that they have received all necessary information and are ready to start their concentrated rehabilitation.

Outcomes

Assessments will be performed before and one week after the concentrated rehabilitation program, and after 3, 6 and 12 months. An overview of the measurement tools and the respective assessment times are presented in Table 2. The outcomes are selected with the aim of describing the overall experiences with the concept of the concentrated treatment format. More detailed, disease-specific outcome measures are also assessed, but will not be presented in this generic protocol paper, as they pertain to other aspects than the concentrated treatment format per se. The initial results will be published following 3 months of follow-up, whereas final results are to be published upon 12 months of follow-up.

Primary outcome measures

Acceptability: The acceptability of the treatment will be measured by the following variables: 1) The proportion of patients accepting to participate in the treatment of those fulfilling inclusion criteria and offered participation, 2) The proportion of patients offered participation that start treatment, and 3) The proportion completing the treatment program (on-site).

The Client Satisfaction Questionnaire (CSQ-8) is an 8-item questionnaire that measures patient satisfaction with health services, where the items are rated from 1 (very low satisfaction) to 4 (very high satisfaction) [23]. The total score ranges from 8-32, with higher scores indicating higher degree

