Data will be analyzed with Stata version 16.1 (StataCorp LLC 2019, College Station, TX, USA). For the initial pilot study, linear mixed models will be used to evaluate changes in the trans-diagnostic primary outcome measures from pre-treatment to post treatment and 3-months follow-up. Between illness differences in measured change will be explored by including interactions between time (pre-treatment, post-treatment, and 3-month follow up) and illness. Statistically significant interactions will be followed by examination of simple effects. Within-group effect sizes will be calculated on complete data using Glass' Δ , with pretreatment SD as denominator. Glass's Δ is the recommended effect size for intervention studies in which there are reasons to believe that the treatment will influence the standard deviation as well as the mean [34]. An effect size is commonly interpreted as small (0.2), moderate (0.5), and large (0.8)

Following the principle of intention-to-treat, all participants will be included in the analyses, irrespective of missing data at any of the assessment points. Mixed models do not assume balanced data and are able to account for missing data on the outcome variable by using all available data on each participant. Under the *missing at random* (MAR) assumption, these models provide unbiased estimates [35].

Clinically significant change will be assessed using the criteria of Jacobson and Truax (1991). These specify that 1) The patients' pre-post (pre-follow-up) change score on the primary outcome measures is larger than the measurement error (Reliable Change Index) and 2) The post-treatment (follow-up) score is outside of the patient sample's pre-treatment distribution (defined as $M - 2SD$) or within the normal group's distribution (defined as $M + 2SD$).

Data collection and monitoring:

For each illness, a centralized team will be established. This team will have monthly contact with one designated researcher for each illness in order to monitor inclusion and data collection. Most of the data will be collected electronically and all sensitive data stored on an encrypted server at Helse Vest IKT. Once the patients are included, all data entered by participants are monitored by the Study Administrative Team.

Adverse events

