The study is designed with participants as their own controls (pre-post comparisons) with a 12-month follow-up. Although this allows for summarizing the experiences and findings as described above, causal conclusions on the effects of the intervention may not be drawn. However, in our mind, this is an essential first step enabling subsequent separate controlled trials where such research questions – as well as the cost-effectiveness issues – may be addressed. Still, the modest labor factor (ten patients, two group leaders) compared to traditional rehabilitation projects clearly benefit our concentrated treatment format, if shown to be efficacious.

If the intervention is followed by meaningful improvements for the participants, we will be able to help large groups of patients with chronic illnesses to adhere to choices in their daily living that eventually will enhance their functional status. Due to the concentrated format, the fact that participants need only 3 or 4 days of sick leave to take part in the intervention, with the continued rehabilitation process at home is another clear advantage. Existing rehabilitation programs for chronic illnesses often have a duration of 3-4 weeks or longer, and therefore requires longer time away from home and for those who are working, longer sick leave. Another benefit of our intervention is the focus on implementing micro-choices in everyday life, with guided practice during the intervention and the assisted introduction into the life at home and work. Although this needs to be investigated, the aim is to ensure the long-term maintenance of the new life trajectory.

Considering the methodology, dropouts and poor adherence to the intervention can threaten the internal validity. Although proper information aims to limit this problem, we cannot be sure that the participants will participate for the whole period or whether they will complete digital and clinical

examinations at 3- 6- and 12-month follow-ups. A notice will be sent to the patients about two to three weeks before the assessments will take place. Participants who are not answering the questionnaires online, or meet to the clinical examinations, will be contacted by telephone. Impact of missing data will be assessed with appropriate statistical methods, e.g., linear mixed models, multiple imputations, and sensitivity analysis.

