
 Type 2 diabetes Age >18 years Have at least one of the following complications/challenges: 
 Dysglycemia Frequent or severe hypoglycemia Weight gain Diabetes complications Diet, physical activity and/or medical treatment challenges 	
 Type 1 diabetes Monogenic diabetes Secondary diabetes (pancreatogenic or any other forms of secondary diabetes). Ongoing pregnancy
Post-COVID-19 Symptoms	

 Age between 18–67 years >2 months since the COVID-19 infection Impaired ability to work full-time Substantial post-COVID-19 related physical and/or mental health problems 
 Fatigue Dyspnea Concentration difficulties Sleeplessness, diurnal disturbances Nutritional deficiencies 	
 Exercise contraindicated
Anxiety or depression	

 Age between 18- 47 years Fulfilling ICD-11 criteria for one of the following disorders: 
 Mixed anxiety and depressive illness Other mixed anxiety illnesses Unspecified anxiety illness Generalized anxiety illness Depressive episode Recurrent depression Unspecified recurrent depression 	
 Bipolar illness Psychosis Ongoing substance abuse/dependence Ongoing suicidal ideation

Abbreviations: PCR: polymerase chain reaction; ICD: International Classification of Illnesses

Table 2. Questionnaires, clinical and physical examinations

Questionnaires and assessments	Assessment point
• Client Satisfaction Questionnaire	• One week post rehabilitation
• Brief Illness Perception Questionnaire	• Baseline, one week, 3-, 6- and 12-months post rehabilitation
• Work and Social Adjustment Scale	• Baseline, 3-, 6- and 12-months post rehabilitation
• Strategies for handling symptoms, rating 0-100 and two questions ¹	• Daily reports for 21 days post rehabilitation
• Patient Activation Measure	• Baseline, one week, 3-, 6- and 12-months post rehabilitation
• Consumption of health care	• Baseline, 3-, 6- and 12-months post rehabilitation
• Medication lists	• Baseline, 3-, 6- and 12-months post rehabilitation
• Body weight/body mass index	• Baseline, 3-, 6- and 12-months post rehabilitation

¹ To what extent did you allow the symptoms to decide today" (0-10) and "To what extent did you make use of the principle of 'doing something else'" (0-10).

References

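### Glass' delta is computed on complete data while the same change is modelled on all available data; a model-based delta would be a minor, cheap improvement

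*Combined protocol and SAP*

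**What the plan says.** The section on the statistical analysis plan and data handling evaluates change in the trans-diagnostic primary outcomes, from pre-treatment to post-treatment and 3 months, by linear mixed models with time-by-illness interactions. It includes every participant whatever is missing. It says mixed models are "able to account for missing data on the outcome variable by using all available data on each participant" and that, under missing at random (MAR), "these models provide unbiased estimates".

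The same section sets a different data set for the effect size: "Within-group effect sizes will be calculated on complete data using Glass' Δ , with pretreatment SD as denominator". It attaches the usual small, moderate and large labels (0.2, 0.5, 0.8). It does not say whether complete data means all visits or only the two visits of a contrast, nor whose pretreatment SD is the denominator.

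The Discussion says that "dropouts and poor adherence to the intervention can threaten the internal validity" and describes advance notices and telephone contact with non-responders. It adds: "Impact of missing data will be assessed with appropriate statistical methods, e.g., linear mixed models, multiple imputations, and sensitivity analysis". None of these methods is tied to delta.

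In Table 2 the Brief IPQ has a one-week score. The WSAS is scheduled at "Baseline, 3-, 6- and 12-months post rehabilitation", so it has none. The CSQ-8 is given once and has no change score. The point therefore concerns the Brief IPQ and the WSAS.

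**The concern.** One change would be reported twice, from two sets of patients. The model uses partial records and is protected against dropout that depends on observed scores. The complete-data delta is not: it describes those who stayed. If severe patients leave, or those with little early benefit leave, the stayers' mean change differs from that of everyone who started, and their baseline SD can differ too.

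It matters to a modest degree. One aim is to "describe basic changes in functional status", delta is the figure that carries the size labels, and "The initial results will be published following 3 months of follow-up". A reader may then see two figures for one change that do not match.

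**Working it through.** **Plan's own figure.** There is none to reproduce: the documents give no effect size, SD, correlation or dropout rate.

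**Inputs.** From the documents: 40 to 50 patients per illness (study design; 45 used here) and the visit schedule in Table 2. Assumed: unit SDs; improvement of 0.50 SD at one week and at 3 months; correlation 0.6 between baseline and each later visit, 0.7 between one week and 3 months; scores missing at 3 months only; logistic dropout with slope 0.5 to 1.0 per SD of the driver. As only the 3-month score can be missing, the all-visits and paired-visits meanings of complete data coincide.

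**Formula for baseline-related dropout.** With b the slope of follow-up on baseline:

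bias in completers' mean change = (b − 1) × (completers' mean baseline − everyone's mean baseline).

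This is zero only if b = 1 or the baseline means agree. Here b = 0.6.

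**Numbers at 20% missing, slope 1.0** (higher score = worse; baseline means and SDs from 2,000,000 simulated patients):

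- Severe patients lost: completers' mean baseline is −0.174. Bias = (0.6 − 1) × (−0.174) = +0.070, so change = −0.50 + 0.070 = −0.430. Delta is 0.43 with the SD of all participants (1.0) and 0.430/0.943 = 0.46 with the completers' SD.
- Mild patients lost: mean baseline is +0.173. Bias = (0.6 − 1) × 0.173 = −0.069, so change = −0.569. Delta is 0.57 with the SD of all, and 0.569/0.942 = 0.60 with the completers' SD.

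**3-month delta at 20% missing, slopes 0.5 to 1.0** (repeat runs agree within about 0.01):

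| Dropout driven by | Complete data, completers' SD | Complete data, SD of all | Three-visit unstructured model |
|---|---|---|---|
| High baseline severity | 0.46–0.47 | 0.43–0.46 | 0.50 |
| Low baseline severity | 0.55–0.61 | 0.54–0.57 | 0.50 |
| Poor early change | 0.56–0.61 | 0.56–0.60 | 0.50 |
| Poor one-week score | 0.51–0.53 | 0.51–0.52 | 0.50 |

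If dropout is completely at random, both approaches give 0.50. With a random intercept only, the three-visit model gives 0.50–0.52 in these cases. At 10% missing the complete-data biases are about 0.01–0.06. At 30% the completers'-SD version ranges from 0.43 to 0.65.

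**Against sampling error.** The standard error of delta at n = 45 is 0.165–0.176. The largest bias in the table is 0.61 − 0.50 = 0.11, and 0.11/0.165 = 0.67 of a standard error.

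**Disagreement in one sample** (n = 45, 20% missing, completers' SD). The two deltas differ by more than 0.10 in 8% of samples when dropout is completely at random, 9–14% if severe patients are lost, 22–47% if mild patients are lost and 22–48% after poor early change.

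**WSAS, baseline and 3 months only, 20% missing.** The two-visit model gives 0.50 for baseline-related dropout and 0.54–0.57 after poor early change (complete data, completers' SD, 0.56–0.61). After a poor one-week score it gives 0.53–0.56, further from 0.50 than the complete-data 0.51–0.53.

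**Missingness that depends on the unseen 3-month score.** Every version is biased at 20%, between about 0.54 and 0.62.

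**The case against.** The strongest reply is that little hangs on this. The study is an uncontrolled pilot that disclaims causal conclusions. Delta stands beside the mixed-model estimates, not in place of them, and feeds no test or decision rule. Reminders and telephone contact may hold missingness nearer 10% than 20%. All of this stands, and it makes the point minor. It does not remove it: the plan already fits a model that yields a less biased numerator, and the general list of missing-data methods in the Discussion does not reach delta.

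A second reply is that the model is not always better. That is right for the WSAS, the scale closest to functional status. Without a one-week score, its model-based delta can do worse than the complete-data one. This is a reason to report both.

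Three stronger readings are tempting and are not supported:

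- A reader might infer that the SAP contradicts itself or wrongly claims unbiasedness for delta. It does not: the MAR statement is confined to the models, and the delta sentence openly names its data set.
- A reader might infer that complete-data delta will flatter the treatment. The direction depends on who leaves, which the documents do not tell us.
- A reader might infer that the significance tests are affected. They rest on the models, not on delta.

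**Conclusion.** The point holds as a minor, low-cost improvement. Under dropout related to baseline severity or early change, complete-data delta is biased and can differ visibly from the model's estimate. In the illustration the bias is at most about 0.11 at 20% missing and about 0.01–0.06 at 10%, always below one standard error per illness. These sizes rest wholly on the assumed effect, correlations and dropout patterns, and they shift with the choice of SD, which the SAP leaves open. The advantage of a model-based delta is clear for the Brief IPQ. For the WSAS it is clear only when dropout is related to baseline. No version is protected if missingness depends on the unobserved score.

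**What to change.** Replace the delta sentence in the SAP with:

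> For each illness and visit, Glass' delta is the mixed-model estimated mean change from pre-treatment divided by the pretreatment SD of all participants in that illness with a baseline score. Delta for participants with both the baseline score and that visit's score is also reported, with n per visit, as a sensitivity figure.

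Add:

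> WSAS has no one-week score in Table 2; its model-based delta corrects for baseline-related dropout, but may be no better than the paired-completer delta if dropout depends on one-week status. Neither version is unbiased if missingness depends on the unobserved score.

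No confidence interval is required for this. If one is reported, the standard error of the change should come from a model with illness-specific variances, because a pooled variance would be matched with an illness-specific SD. The SAP should also say that the interval treats patients as independent although treatment is given in groups. In simulation, with 5% of follow-up variance shared within groups (5 groups of 9), a nominal 95% interval covered about 90%.

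Cost: SAP wording, a few lines of code and one extra reported figure, with no new data. The downside is some dependence of the lead figure on the model's covariance structure, which should be reported. At the least, the SAP should define complete data and say whose pretreatment SD is used.

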of satisfaction. The CSQ-8 has good psychometric properties, with high internal consistency (Cronbach's $\alpha = .93$), and high inter-item correlation [24].

The Brief Illness Perception Questionnaire (Brief IPQ) is a 9-item questionnaire designed to assess cognitive and emotional representations of illness [25]. Questions are graded from 1 to 10. The last item deals with perceived cause of illness, in which respondents list the perceived three most important causal factors in their illness. For this questionnaire, the general word 'illness' can be replaced by the name of a particular illness. The word 'treatment' in the treatment control item can be replaced by a particular treatment such as 'surgery' or 'physiotherapy'. The scale has good psychometric properties according to a recent review [26].

The Work and Social Adjustment Scale (WSAS) is a short questionnaire measuring the impact of the illness on aspects of work and social activities [27]. The scale consists of five items rated from 0 (not at all) to 8 (very severe), and higher score indicates higher impairment (maximum score is 40). The scale is regarded as reliable and valid, with good psychometric properties.

Trans-diagnostic secondary outcome measures: At pre- and post-treatment and the follow-up assessments the patients will be asked to rate on a scale from 0-100 to what extent they use the following strategies when trying to handle the symptoms:

- a) Wait to start an activity until I feel up to it
- b) Wait to start an activity until I am certain that I will succeed
- c) Ensure that the symptoms will not get worse
- d) Ensure that I am prepared to handle challenges
- e) When I get anxious I try to calm down before I proceed
- f) Spend a lot of time on worrying and ruminating
- g) Avoid socializing if I do not feel up to it
- h) Ensure that I get enough rest
- i) Try to not let others see how I feel
- j) Try to have a positive mindset
- k) Follow my gut feeling

The intervention

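### The clinically-significant-change rule does not require a patient to start outside the normal range, so patients who never left that range can be counted

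*Combined protocol and SAP*

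**What the plan says.** The rule is in *Statistical analysis plan (SAP) and data handling*, under the Jacobson-Truax criteria. It has two conditions joined by 'and'; the closing digit of this quote numbers the second: "change score on the primary outcome measures is larger than the measurement error (Reliable Change Index) and 2". The second condition is "The post-treatment (follow-up) score is outside of the patient sample's pre-treatment distribution", defined as M-2SD, "or within the normal group's distribution", defined as M+2SD.

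The SAP does not name the normal group or give its mean and SD. It gives no reliability for the RCI and does not say whether the patient M and SD are pooled or taken per illness. It says nothing about patients who are already inside the normal range at baseline.

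*Primary outcome measures* fixes the WSAS direction and range: "higher score indicates higher impairment (maximum score is 40"), from five items scored 0 to 8. Its reliability is given in words only: "The scale is regarded as reliable and valid, with good psychometric properties". The same holds for the Brief Illness Perception Questionnaire (Brief IPQ): "The scale has good psychometric properties according to a recent review". Table 1 sets no minimum score on either scale for any illness.

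**The concern.** The second condition adds something to reliable change only if it marks a move from one range to another. As written it looks at the final score alone. A patient who begins inside the normal range, improves by more than the RCI and ends inside it satisfies both conditions, and is reported as clinically significantly changed without having been on the impaired side of the limit used.

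The eligibility criteria make this plausible, and unequal between illnesses. Low back pain requires months of sick leave and post-COVID-19 requires reduced ability to work full-time. Type 2 diabetes can qualify through weight gain or difficulty with diet alone. If baseline WSAS differs accordingly, the percentage would contain different shares of patients who were in range all along, in a study that sets out to compare change between illnesses.

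**Working it through.** The plan states no rate, cut-off, RCI, mean, SD or norm, so there is no figure of its own to reproduce.

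**1. What the 'or' does.** On a scale where lower is better, a score at or below either limit is simply a score at or below the higher of the two. The rate therefore equals the rate under the more lenient limit, and the stricter limit has no effect.

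**2. When M-2SD drops out on the WSAS.** M - 2SD <= 0 exactly when SD >= M/2. With assumed mean/SD: 16/8 gives 16 - 16 = 0; 20/10 gives 0; 20/8 gives 4; 24/8 gives 8. Where the limit is below 0 no score can pass it. Where it is exactly 0, a score of 0 might pass, but it also passes the normal limit, so only that limit matters.

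**3. When an in-range patient can be counted.** The score cannot fall below 0, so someone starting at or below the operative limit can improve by more than the RCI only if that limit exceeds the RCI. With SD 8 and assumed reliability 0.8, RCI = 1.96 x sqrt(2) x 8 x sqrt(0.2) = 9.92. Norm 2/2 gives 2 + 4 = 6, below 9.92, so nobody. Norm 4/5 gives 14 and norm 6/6 gives 18, so some can.

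**4. Share in range at baseline** (normal scores rounded to whole points, limit inclusive):
- 20/8, limit 18: Phi((18.5 - 20)/8) = 42.5%
- 16/8, limit 18: Phi((18.5 - 16)/8) = 62%
- 24/8, limit 14: Phi((14.5 - 24)/8) = 12%

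**5. Simulated rates.** Every input is an assumption: bivariate normal scores, rounded and limited to 0-40, reliability 0.8, pre-post correlation 0.5, gain 0.8 SD. 'Crossing' means the rule as written plus a baseline score above the limit. The denominator is all patients.

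| Baseline | Norm | Reliable change alone | Rule as written | With crossing | Already in range |
|---|---|---|---|---|---|
| 20/8 | 6/6 | 34% | 30.6% | 23.8% | 6.8 points |
| 16/8 | 6/6 | 33% | 31.4% | 19.6% | 11.8 points |
| 24/8 | 4/5 | 34.5% | 19.4% | 18.6% | 0.8 points |
| any above | 2/2 | - | - | same as the rule | 0 |

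With 40-50 patients per illness, 6.8 points is 2.7-3.4 patients and 11.8 points is 4.7-5.9 patients. As a share of those counted, 6.8/30.6 = 22%, 11.8/31.4 = 38% and 0.8/19.4 = 4%.

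**6. Wider range.** A separate set of 64 assumed scenarios used correlation 0.6, reliability 0.8 or 0.9, gains of 0.5 or 0.8 SD, and norms from 2/2 to 6/6. Patients already in range made up 0-21.5% of the sample among those counted, that is 0-48% of those counted. The rule as written ran from 3.9% to 44.3%.

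**The case against.** The best defence is that the RCI is a real filter. Being in range at baseline is not enough, since the patient must also improve beyond measurement error, and with a low normal limit nobody in range can. That stands, and it is why the effect runs from nil to large. It does not rescue the rule where the normal limit lies near the patients' baseline mean.

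It is also fair that this is a descriptive addition. No main hypothesis refers to it, the mixed models carry the analysis of change, and the Discussion already rules out causal conclusions. That limits the weight of the point.

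A reader might infer more than the documents support:
- **That M-2SD is nearly unattainable and the normal limit always lenient.** No means or norms are given, and the order can reverse: at 24/8 with norm 2/2, M-2SD is 8 and the normal limit is 6.
- **That the rate depends on which branch the analyst picks.** Read literally, the 'or' leaves no choice; the lenient limit decides.
- **That the WSAS rate always collapses to plain reliable change.** It nearly does with norm 6/6 at 20/8 (31% against 34%), but not at 24/8 with norm 4/5 (19.4% against 34.5%).
- **That the Brief IPQ can have no normal group.** It is "designed to assess cognitive and emotional representations of illness", so a comparison sample of people without illness is not obvious, but the documents do not say that none exists.

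**Conclusion.** The flaw is in the stated rule and is more than missing detail: followed exactly, it can label as clinically significantly changed a patient who was never on the impaired side of the limit. That reading needs no assumed numbers. The size does: about 7 of 31 points or 12 of 31 where the normal limit is close to or above the patients' baseline mean, under 1 point or none where it is well below. The true position in that range cannot be known until a normal sample is named and baseline scores are seen.

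It would be tempting to add that the correction must lower the rate. That holds only with all patients in the denominator, where the rate falls or stays the same. Dropping in-range patients from the denominator as well can raise it: at 20/8 with norm 6/6, 23.8/(100 - 42.5) = 41.4%, above the 30.6% under the present rule. This is an inexpensive improvement to a descriptive measure and does not affect the mixed-model analysis.

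**What to change.** Amend the SAP before analysis as follows:

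- Count a patient only if the change exceeds the RCI and the score crosses the cut-off, from the impaired side at baseline to the other side at follow-up.
- Fix one cut-off per measure. Name the normal sample with its mean and SD, state the reliability used in the RCI, and say whether the patient M and SD are pooled or per illness.
- Keep all patients in the denominator. Beside the rate, report the number already in range at baseline and the plain reliable-change rate, for each illness.
- Where no suitable normal sample exists for a measure, report reliable change only.

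The SD-weighted midpoint between the patient and normal distributions is an option for the cut-off, not a required correction. If computed from each illness's own baseline it moves between illnesses: with norm 6/6, from 10.3 at 16/8 to 13.7 at 24/8.

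The cost is a few lines of SAP text, a search for a normal sample, and a rate that is the same or lower. No new data are needed.
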